3.3.5.2 Procedures for discontinuation

Patients who discontinue should always be asked about the reason(s) for their discontinuation and the presence of any AEs. If possible, they should be seen and assessed by an investigator(s). AEs should be followed up; diary cards and investigational products should be returned by the patient.

Patients discontinuing due to an AE will be asked to provide a blood sample for assessment of plasma concentrations (see section 4.5.1) at the next visit in conjunction with completion of other protocol specified procedures. In addition, the time of last intake of study medication along with an accurate time of obtaining the blood sample should be recorded.

Patients with an increased serum creatinine will have their metformin held and a repeated serum creatinine test within one week. If this repeated serum creatinine still is increased, despite temporary coexisting contributing factors have been overcome, the patient should discontinue the clinical study.

Randomized patients in the Randomized treatment period (Period C) who do not complete the entire study should complete the procedures described for Visit 13 (end of Period C). Randomized patients in the Extension period (Period D) who do not complete the entire study should complete the procedures described for Visit 17 (end of Period D).

3.3.5.3 Procedures for handling incorrectly enrolled patients

Patients not meeting the inclusion/exclusion criteria for the study should, under no circumstances, be enrolled into the study - there can be no exceptions to this rule. Where patients not meeting the study criteria are enrolled in error or incorrectly randomized, procedures for discontinuation of such patients should be followed.

3.3.5.4 Criteria for entering the action plans

If any of the following criteria is fulfilled, the patients must enter the action plan, Appendix D or E, respectively.

Absolute lymphocyte count \leq 500 cells/ μ L, see Appendix D.

Thrombocyte count <75 000 cells/µL, see Appendix E.

3.4 Treatments

3.4.1 Identity of investigational products and additional drug

The following investigational products and additional drug will be supplied by Bristol-Myers Squibb Pharmaceutical Research Institute. The tablets may contain lactose, which may cause discomfort in lactose-intolerant individuals

Treatment	Dosage form and strength	Manufacturer
Saxagliptin	Plain, yellow, biconvex, round, film coated tablet, 5 mg	Bristol-Myers Squibb
Placebo for saxagliptin	Plain, yellow, biconvex, round, film coated tablet to match saxagliptin 5 mg	Bristol-Myers Squibb
Glipizide	Opaque grey, size 0, two piece, hard gelatine capsule containing commercial glipizide, 5 mg	Commercial drug manufactured by Generics and encapsulated by Fisher
Placebo for glipizide	Opaque grey, size 0, two piece, hard gelatine capsule containing white to off-white powder to match glipizide 5 mg	Fisher
Glucophage [®] (metformin hydrochloride)	Filmcoated, white to off-white round tablet, 500 mg	Merck Serono

3.4.2 Doses and treatment regimens

The blinding is ensured by using double-dummy technique. The investigational products saxagliptin or placebo and glipizide or placebo will be taken orally, immediately before or together with a meal. Saxagliptin or placebo should be taken once daily and glipizide or placebo should be taken once or twice daily depending on the dose directed by the investigator. The investigational product should be taken at approximately the same time of the day during the study period. Patients should be instructed to abstain from all food for 8 hours prior to each clinical visit; however, drinking water is allowed. In the morning prior to each visit, acceptable concomitant medications can be taken with water only.

- Matching placebo tablets for saxagliptin 5 mg oral for the 2-week placebo lead-in period, the 52-week double-blind period and the 52-week double-blind extension period.
- Matching placebo capsules for glipizide (sulphonylurea) 5 mg oral for the 2-week placebo lead-in period, 52-week double-blind period (dosing 5 to 20 mg) and the 52-week double-blind extension period (dosing 5 to 20 mg).
- Saxagliptin tablets 5 mg oral for the 52-week double-blind period and the 52-week double-blind extension period.
- Glipizide (sulphonylurea) 5 mg capsule oral (dosing 5 to 20 mg) for the 52-week double-blind period and the 52-week double-blind extension period.

• Open-label metformin 500 mg tablets oral at a daily dose of 1500 mg - 3000 mg tablets from Visit 2 throughout the study period.

During the lead-in period, each patient will receive one single-blind kit with:

1 bottle containing 35 tablets of placebo to match saxagliptin and 1 bottle containing 140 capsules of placebo to match glipizide

Each patient will during the randomized treatment receive from 1 up to 3 double-blind kits at each visit with:

1 bottle containing 35 tablets of saxagliptin 5 mg and 1 bottle containing 140 capsules of placebo to match glipizide,

or

1 bottle containing 35 tablets of placebo to match saxagliptin and 1 bottle with 140 capsules of glipizide 5 mg.

or

1 bottle containing 35 tablets of placebo to match saxagliptin and 1 bottle with 140 capsules of placebo to match glipizide.

During the titration period the patients will titrate either active or placebo glipizide. Each patient will also receive open-label boxes with 100 tablets of metformin 500 mg, 1 to 7 boxes at each visit.

See Section 3.1 for titration procedures of glipizide.

Treatment doses:

Saxagliptin 5 mg: Morning dose: 1 tablet. Evening dose: N/A

Glipzide 0 mg (placebo). Morning dose: 1 capsule. Evening dose: N/A

Glipizide 5 mg: Morning dose: 1 capsule. Evening dose: N/A

Glipizide 10 mg: Morning dose: 2 capsules. Evening dose: N/A

Glipizide 15 mg: Morning dose: 2 capsules. Evening dose: 1 capsule

Glipizide 20 mg: Morning dose: 2 capsules. Evening dose: 2 capsules

The following guideline should be used if metformin therapy must be modified due to available open-label drug supply.

Current metformin therapy at Visit 2

Metformin dose (500 mg tablets)

1500 - 1999 mg	1500 mg (3 tablets)
2000 – 2499 mg	2000 mg (4 tablets)
2500 – 2550 mg	2500 mg (5 tablets)
>2550 mg	3000 mg (6 tablets)

3.4.3 Labelling

Packing of the investigational product will be carried out by Bristol-Myers Squibb, AstraZeneca and Contract Research Organization (CRO) in accordance with current Good Manufacturing Practice (GMP). Labelling of the investigational product will be carried out by AstraZeneca or CRO in accordance with current GMP. The labels will be translated into local language in accordance with local regulations for each participating country.

All investigational products will be packed in bottles. The saxagliptin/placebo bottles will contain 35 tablets and the glipizide/placebo bottles will contain 140 capsules. One bottle of each type will be placed into a clampacks to form a kit. The bottles will be labelled with labels or booklets, depending on availability, without a tear off part. The labels will fulfil GMP Annex 13 requirements and local regulatory guidelines.

3.4.4 Storage

All investigational products must be kept in a secure place under appropriate storage conditions. A description of the appropriate storage conditions is specified on the investigational product labels and in the IB.

3.5 Method of assigning patients to treatment groups

After written informed consent has been obtained the patient will be assigned an E-code (country, centre, and patient specific). Patient eligibility will be established before treatment randomization. Patients will be randomized strictly sequentially, as patients are eligible for randomization.

Randomization to study treatment will be done via IWRS on Visit 3 in balanced blocks in order to ensure approximate balance among treatment groups.

The E-code will be used to identify the patient throughout study participation.

The number and size of tablets and capsules distributed will be identical for the 2 treatment arms. Clinical supplies will contain a kit number that is allocated to the treatment arm through a separate randomization and will be used to provide kits of packaged drugs to the centres. The IWRS will sequentially allocate the treatment through the AstraZeneca prepared randomization scheme and provide the randomization number and the appropriate kit number from those available at the centre for the treatment assignment. The Randomization Code will be prepared by study statistician and available for IWRS use.

The randomization is carried out at the study level and the assigned randomization number and the associated kit numbers will not be sequential within a centre. Forced randomization is not allowed. If a patient is dispensed with a wrong drug supply, the patient should continue to take the medication with no attempt to correct the error. The IWRS company will be informed, if possible. The randomization system will ensure balance approximately between groups.

If a patient discontinues from the study, the patient E-code or patient randomization number will not be reused, and the patient will not be allowed to re-enter the study.

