Eligible patients will be given placebo in a single-blind fashion (blind to the patient only) at Visit 2 and start open-label metformin during the 2-week lead-in period. Patients on metformin will be treated with 1500, 2000, 2500 or 3000 mg of open-label metformin for the

duration of the study (see Section 3.4.2 for metformin doses to be used). The aim is that the open-label metformin dose should remain stable throughout the study.

The patients will be counselled on dietary and life-style modifications according to usual clinical routine. A glucometer and a patient diary will be handed out and the patients will be instructed to monitor their blood glucose at least every second day. Information about hypoglycaemic events should be entered into the patient diary.

Visit 2 should preferably be done at the clinic, but may be performed as a telephone visit if it is clear before the scheduled visit that the patient is not eligible due to the laboratory results from Visit 1.

Randomized treatment period (Period C):

The patients will be randomized at Visit 3 (baseline) and the double-blind treatment period will start. Either saxagliptin 5 mg plus open-label metformin or glipizide 5 mg plus open-label metformin will be given using a double-dummy technique. During the randomized treatment period dietary and life-style modification will be reinforced.

Titration period (Visits 4-9)

Patients in the glipizide plus metformin arm will be titrated to optimal effect (FPG \leq 6.1 mmol/L, \leq 110 mg/dL) or the highest tolerable dose during 18 weeks. Glipizide (4 doses) will be initiated at 5 mg per day (morning dose), and titrated in 3-week intervals to a maximum of 20 mg per day. The titration steps will be 10 mg per day (morning dose) followed by 15 mg per day (10 mg as morning dose and 5 mg as evening dose) and 20 mg (10 mg as morning dose and 10 mg as evening dose). In patients for whom titration was not medically indicated at Week 3, re-assessment for titration will occur at Week 6, 9, 12, 15, and 18. The decision for titration will be based on FPG measured at the study centre, using a glucose analyser provided by AstraZeneca. The investigational product (IP) glipizide can be down-titrated once during the titration period if hypoglycaemic events occur. Treatment may thereafter be up-titrated once during the titration period.

Patients on saxagliptin will remain on 5 mg throughout the study, no titration will be possible.

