Assessment of glycaemic parameters (based on results from central laboratory) will be done to determine if criteria for discontinuation are met during the period.

The patients will be instructed to monitor their blood glucose at least every second day. Hypoglycaemic events should be entered into the patient diary. The evaluation at each of the titration visits and final decision by the investigator on dose increase (or decrease) should take into account both the plasma glucose measurements made by the patients prior to visits and the investigator's measurements at the titration visits.

Maintenance treatment period (Visits 10-13)

After the titration period, the patient will return for visits to assess efficacy and safety of the treatment. At any time during the study, investigational product glipizide can be down-titrated to mitigate recurrent hypoglycaemic events at the discretion of the investigator, no up-titration is allowed. The patients will continue to monitor their blood glucose at least once a week. Hypoglycaemic events should be entered into the patient diary. Assessment of glycaemic parameters (based on results from central laboratory) will be done at each visit to determine if criteria for discontinuation are met during the period.

Randomized patients in the Titration or Maintenance treatment period who do not complete the entire study should complete the procedures described for Visit 13 (end of Period C).

Extension period (Period D) (Visits 14-17)

After 52 weeks, eligible patients will continue in the randomized extension treatment period with the same treatment given at the end of Period C. The patient will return for visits approximately every thirteenth week to assess efficacy and safety of the treatment. The patients will continue to monitor their blood glucose at least once a week. Hypoglycaemic events should be entered into the patient diary. At any time during the study, investigational product glipizide can be down-titrated to mitigate recurrent hypoglycaemic events at the discretion of the investigator, no up-titration is allowed. Assessment of glycaemic parameters (based on results from central laboratory) will be evaluated at Visit 14 to 16 to determine eligibility for discontinuation during the period. The patients will stop taking investigational product at the end of treatment visit, Visit 17.

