3.3.5 Discontinuation of patients from treatment or assessment

3.3.5.1 Criteria for discontinuation

Patients may be discontinued from study treatment and assessments at any time. Specific reasons for discontinuing a patient from this study are:

- 1. Voluntary discontinuation by the patient who is at any time free to discontinue his/her participation in the study, without prejudice to further treatment.
- 2. Safety reasons as judged by the investigator, AstraZeneca and/or Bristol-Myers Squibb Pharmacovigilance.
- 3. Severe non-compliance to protocol as judged by the investigator and/or AstraZeneca.
- 4. Incorrect enrolment or randomization, ie, the patient does not meet the required inclusion/exclusion criteria for the study.
- 5. Patient lost to follow-up (as defined by, unable to reach the patient after 3 documented phone calls, fax, e-mail, or attempts to contact him/her through patient

locator agencies (if allowed per national regulation) and having sent one letter by registered/certified mail; all should be documented in the patients medical records).

Study specific discontinuation criteria are listed below. The FPG and HbA1c values will be measured at the central laboratory.

- 6. Use of (need for) any antihyperglycaemic medication other than investigational product or open-label metformin for more than 14 consecutive days, however insulin during hospitalisation is allowed.
- 7. Treatment with chronic systemic glucocorticoids. However, two temporary periods no longer than 7 days each are allowed.
- 8. Severe and/or frequent hypoglycaemic events, defined as ≥ 1 major event or recurring minor events and the possibility of down-titration and contributing factors (eg, excessive physical activity) has been evaluated.
- 9. Patients whose double blind treatment codes are broken by the investigator.
- 10. Pregnancy.
- 11. FPG >15.0 mmol/L (>270 mg/dL) at Visit 4 (Week 3) confirmed at a repeated measurement.
- 12. FPG >13.3 mmol/L (>240 mg/dL) at Visit 7 (Week 12) and on maximum titrated tolerated dose for at least two weeks confirmed at a repeated measurement.
- 13. FPG >12.2 mmol/L (>220 mg/dL) at Visit 9 (Week 18) and on maximum titrated tolerated dose for at least two weeks confirmed at a repeated measurement.
- 14. FPG >11.1 mmol/L (>200 mg/dL) at Visit 10 (Week 24) confirmed at a repeated measurement.
- 15. HbA1c >8.0% at Visit 11 (Week 30) and Visit 12 (Week 39).
- 16. HbA1c >7.5% at Visit 13 (Week 52), Visit 14 (Week 65) and Visit 15 (Week 78).

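### Section 3.5 orders a noticed wrong drug supply to be continued uncorrected, even a kit of the other arm; a sham-titrated saxagliptin patient would then stay on a first glipizide dose of 10, 15 or 20 mg/day

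*Protocol*

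**What the plan says.** Section 3.5 covers a wrong drug supply in two sentences. The first says that "the patient should continue to take the medication with no attempt to correct the error". The second says that the IWRS company is told, if possible. The rule does not distinguish a wrong kit of the patient's own arm from a kit of the other arm. It also does not say whether later kits return to the assigned arm.

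The dosing rules are in Sections 3.1 and 3.4.2:

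- Start and steps: "Glipizide (4 doses) will be initiated at 5 mg per day (morning dose), and titrated in 3-week intervals", up to 20 mg per day (Section 3.1).
- Sham titration: "During the titration period the patients will titrate either active or placebo glipizide" (Section 3.4.2).
- The glipizide-arm kit: "1 bottle containing 35 tablets of placebo to match saxagliptin and 1 bottle with 140 capsules of glipizide 5 mg" (Section 3.4.2). Its tablets are placebo, so it also stops saxagliptin.
- Capsule counts: 2, 3 or 4 capsules a day at the three upper levels, for example "Glipizide 20 mg: Morning dose: 2 capsules. Evening dose: 2 capsules" (Section 3.4.2).

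Three other provisions bear on the patient's safety. In the titration period glipizide "can be down-titrated once during the titration period if hypoglycaemic events occur". After it, down-titration is allowed "to mitigate recurrent hypoglycaemic events at the discretion of the investigator, no up-titration is allowed". Discontinuation is possible for "Safety reasons as judged by the investigator, AstraZeneca and/or Bristol-Myers Squibb Pharmacovigilance" (Section 3.3.5.1, criterion 2).

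**The concern.** An instruction not to correct an error, and to report it to the IWRS company, presupposes that someone has noticed it. For a wrong kit of the same arm, continuing is harmless and sensible. For a kit of the other arm, the same sentence tells the site to leave the patient on the other treatment.

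The harm is clearest for a saxagliptin patient who has been sham-titrated. The capsule count is already 2, 3 or 4, and with the wrong kit those capsules become active. The patient meets glipizide for the first time at a dose that the protocol otherwise reaches only by steps. Hypoglycaemia with insulin secretagogues is a concern that the protocol itself raises (Section 1.2), and hypoglycaemic events are a key secondary variable (Section 6.2).

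No provision lets the site replace the kit and keep the patient on randomized treatment. Down-titration is linked to hypoglycaemic events. Criterion 2 needs no prior event but ends participation, and a broken code also leads to discontinuation (Section 3.6.2). Section 6.3.5 reassigns actual treatment for patients on the other drug for the whole 52 weeks, but that is an analysis rule and gives no clinical handling.

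**Working it through.** **Dose on the first day of the wrong kit.** Inputs are the 5 mg capsule and the capsule counts of Section 3.4.2, and the 5 mg start and 3-week interval of Section 3.1.

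Dose = capsules per day × 5 mg. This reproduces the plan's own dose list: 1 × 5 = 5, 2 × 5 = 10, 3 × 5 = 15 and 4 × 5 = 20 mg/day.

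Steps skipped = capsules − 1. Time skipped = steps × 3 weeks. The time skipped is also the earliest week at which the sham count can be reached.

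| Sham capsules per day | Earliest week | First glipizide dose | Multiple of 5 mg start | Steps skipped |
|---|---|---|---|---|
| 2 | 3 (Visit 4) | 10 mg/day | 2 | 1 (3 weeks) |
| 3 | 6 (Visit 5) | 15 mg/day | 3 | 2 (6 weeks) |
| 4 | 9 (Visit 6) | 20 mg/day | 4 | 3 (9 weeks) |

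**How long one wrong kit lasts.** This assumes that one kit is wrong and that the next visit's kit is of the assigned arm. A kit holds 35 tablets at 1 per day, so 35 days. Its 140 capsules at 4 per day also last 35 days, and at lower counts the tablets run out first. Exposure = min(35 days, gap to the next visit).

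Visit windows from Table 3, in days after Visit 3: Visit 4, 21–28; Visit 5, 39–45; Visit 6, 56–63; Visit 7, 81–87; Visit 8, 105–112; Visit 9, 123–129; Visit 10, 165–171; Visit 11, 205–215; Visit 12, 268–278.

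Shortest gap = earliest later visit − latest earlier visit. Longest gap = the reverse.

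- Visits 4–5: 39 − 28 = 11 to 45 − 21 = 24 days
- Visits 5–6: 56 − 45 = 11 to 63 − 39 = 24 days
- Visits 6–7: 81 − 63 = 18 to 87 − 56 = 31 days
- Visits 7–8: 105 − 87 = 18 to 112 − 81 = 31 days
- Visits 8–9: 123 − 112 = 11 to 129 − 105 = 24 days
- Visits 9–10: 165 − 129 = 36 to 171 − 123 = 48 days
- Visits 10–11: 205 − 171 = 34 to 215 − 165 = 50 days
- Visits 11–12: 268 − 215 = 53 to 278 − 205 = 73 days; all later gaps are at least 77 days

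One wrong kit therefore lasts 11 to 31 days between titration visits (21 days on the nominal schedule) and 34 to 35 days when dispensed at Visit 9 or later. It lasts longer if more than one of the up to 3 kits dispensed at a visit is wrong, or if later kits do not return to the assigned arm.

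**How many patients.** The protocol gives no frequency of wrong kits, so no count is derived.

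**The case against.** The strongest defence is that the sentence protects the randomization and the blind. Sites cannot tell a same-arm error from a cross-arm one, because access to the scheme is confined to the IWRS company and two sponsor departments (Section 3.6.1). A uniform rule is therefore defensible at site level. This part stands, and a rule that made sites stop every wrong kit would interrupt correct treatment in same-arm cases. But keeping the assignment is not the same as keeping the wrong kit. The IWRS company holds the scheme, is already told of errors, and assigns kits from centre stock (Section 3.5), so it can make the distinction without unblinding the site.

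Safeguards also exist. At titration visits the investigator's decision to raise or lower the dose takes patient and site glucose values into account (Section 3.1). A single low reading without symptoms counts as a hypoglycaemic event (Section 4.7.4.1), and self-monitoring is at least every second day in that period. The sham count was guided by fasting glucose, saxagliptin is removed, and the dose stays within 5 to 20 mg. These facts reduce the risk. They do not return the patient to randomized treatment, and after Week 18 they are weaker: monitoring is weekly, and down-titration is for recurrent events and cannot be reversed.

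A reader might infer that the reverse error is equally serious: a glipizide patient takes placebo capsules for one kit and then resumes 10 to 20 mg. The documents do not support that. The patient resumes a dose already titrated, and the protocol elsewhere lets held product be reinstated without prescribing re-titration (Appendices D and E).

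**Conclusion.** The point holds as a badly fixed conduct rule. A noticed cross-arm error is continued by instruction. For a sham-titrated saxagliptin patient this means a first glipizide dose of 10, 15 or 20 mg/day, which is 2, 3 or 4 times the intended start. The dose figures follow from the protocol alone. The durations (11 to 31 days between titration visits, up to 35 days later) depend on one wrong kit and on a return to the assigned arm at the next visit.

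A reader might go further and infer that the confirmatory results are at risk. The documents do not support this: they give no error frequency, and it is probably low. Nor do they show an excess of hypoglycaemia, since they give no event rate for starting glipizide at 10 to 20 mg. The case rests on patient safety and on keeping patients on their randomized treatment. The change is worth making because it is cheap.

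**What to change.** Replace the sentence in Section 3.5 with:

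> The randomization assignment is never changed. If a wrong kit is detected, the site informs the IWRS without delay. The IWRS, which holds the scheme, checks the kit. If it contains the randomized treatment, the patient continues it without interruption. If not, the patient stops it, plasma glucose is checked, and the IWRS assigns a replacement kit of the randomized treatment from centre stock, without unblinding the site. All later kits follow the randomized assignment.

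Leave the titration rules of Section 3.1 unchanged, including the ban on up-titration after Week 18. Relaxing that ban would allow dose changes inside the Week 24 to Week 52 window of the durability slope. Section 6.3.5 needs no change.

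The cost is a small IWRS procedure and one extra site contact per detected error. The site also learns that a replaced kit was of the other arm, but not which arm that is.

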Dispensation of investigational product and/or open-label metformin through IWRS		X	X	X	X	X	X	X	X	X	X	X	X
Dispensation of glucometer and/or supplies/provide instruction		X	X	X	X	X	X	X	X	X	X	X	X
Dispensation of patient diary (if applicable)		X	X	X	X	X	X	X	X	X	X	X	X
Patient diary review for hypoglycaemic events/check glucose values in glucometer			X	X	X	X	X	X	X	X	X	X	X
Drug accountability			X	X	X	X	X	X	X	X	X	X	X
Informed consent and blood sample for genetic research ⁱ			X	\rightarrow	\rightarrow	\rightarrow	\rightarrow	\rightarrow	\rightarrow				

Visit 2 may be performed as a telephone visit if it is clear before the visit that the patient is not eligible due to the laboratory results Randomized patients who do not complete the entire study should complete the procedures described for end of Period C (Visit 13)

- Specification of laboratory parameters are shown in Table 4 and Table 6
- A blood sample and an urine sample will be taken for future analyses
- Pharmacokinetic samples (6 samples per visit) will be taken from 50 of the randomized patients who will undergo OGTT assessment. Note that no OGTT assessment will be carried out at Visit 11.
- One blood sample for plasma concentration of saxagliptin and BMS-510849 will be taken if a patient experiences any predefined AE or discontinues from the study due to an AE (See section 4.7.1.3)
- Pregnancy test will be done on all female patients who are not surgically sterile or postmenopausal
- Extended OGTT will be carried out on patients in a selection of countries (50 patients)
- Genetic informed consent (IC) must be obtained before genetic blood sample is taken, when patient eligibility for the study has been confirmed. Blood sample donation is optional and can be done from randomization Visit 3 to Visit 9.

Table 2 Study plan for Extension period (Period D)

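### Section 3.5 leaves a known wrong kit uncorrected at any visit; for a cross-arm resupply kit this can start glipizide at 10 to 20 mg/day without titration (minor, cheap to fix)

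*Protocol*

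**What the plan says.** Section 3.5 of the Protocol covers assignment to treatment. The IWRS is to "provide the randomization number and the appropriate kit number from those available at the centre". If a wrong supply is handed out, "the patient should continue to take the medication with no attempt to correct the error". The only notification attached is "The IWRS company will be informed, if possible". No visit, duration or type of error is named.

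The supply and dose rules that bear on this are elsewhere:

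- Section 3.1, titration period: "Glipizide (4 doses) will be initiated at 5 mg per day (morning dose), and titrated in 3-week intervals".
- Section 3.4.2: "During the titration period the patients will titrate either active or placebo glipizide". A glipizide-arm kit is "1 bottle containing 35 tablets of placebo to match saxagliptin and 1 bottle with 140 capsules of glipizide 5 mg". The top of the dose table is "Glipizide 20 mg: Morning dose: 2 capsules. Evening dose: 2 capsules".
- Section 3.1, Table 1, has the row "Dispensation of investigational product and/or open-label metformin through IWRS", marked at every visit from Visit 2 to Visit 13. Table 2 continues dispensing at Visits 14 to 16.

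**The concern.** The instruction not to correct makes sense for the allocation itself. A patient who starts on the wrong arm at Visit 3 takes one capsule, and if that capsule is active it is the intended 5 mg start. Swapping treatment later would only add a second change.

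Resupply is different, because replacing a wrong kit restores the randomized treatment. Under the double-dummy design a saxagliptin-arm patient can already be taking several placebo capsules a day. If the next kit comes from the other arm, the same capsule count delivers active glipizide at a multiple of the starting dose. In the reverse case a glipizide patient stops receiving glipizide. Once the site knows the kit number is wrong, the text still tells it to carry on. At stake is a patient's exposure to a known error, chiefly a risk of hypoglycaemia.

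**Working it through.** **Dose.** Capsules per day × 5 mg gives 1, 2, 3, 4 capsules = 5, 10, 15, 20 mg/day, which reproduces the dose table in Section 3.4.2. With 3-week steps from Visit 3, a patient can reach 2, 3 and 4 capsules at Weeks 3, 6 and 9 at the earliest. A cross-arm kit dispensed from then on starts glipizide at 2 to 4 times the 5 mg of Section 3.1.

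**Opportunities.** Dispensing after Visit 3: Visits 4 to 13 = 10 and Visits 14 to 16 = 3, so 13 occasions.

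**How long one kit lasts.** A bottle holds 140 capsules: 140/4 = 35 days, 140/3 = 46.7 days, 140/2 = 70 days. The longest interval is 13 weeks = 91 days. 91/35 = 2.6, so 3 kits, which agrees with the 1 to 3 kits per visit in Section 3.4.2.

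**Days due to the rule.** An error that nobody has noticed continues under any rule. Only the days after discovery count. For one wrong kit, opened when dispensed and found on day d:

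days = max(0, min(visit interval, bottle days) − d)

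| Situation | Found at once (d = 0) | d = 7 | d = 14 | Found at next visit |
|---|---|---|---|---|
| Titration, 21-day interval | 21 | 14 | 7 | 0 |
| After Week 18, 4 capsules/day (interval 42, 63 or 91 days) | 35 | 28 | 21 | 0 |

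Days 7 and 14 are illustrations; the Protocol gives no discovery time.

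**Visit windows (Table 3).** The longest titration interval is from Visit 6 at day 63 − 7 = 56 to Visit 7 at day 84 + 3 = 87, that is 31 days. This is still below the 35-day bottle limit, so the cap in titration is 31.

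**Lower capsule counts after Week 18.** If the patient finishes the capsule bottle before opening another kit, the caps for intervals of 42, 63 and 91 days are 42, 46 and 46 days at 3 capsules, and 42, 63 and 70 days at 2 capsules. The dose in those cases is 15 or 10 mg/day. The kit's tablet bottle holds 35 once-daily tablets, so a patient who moves to the next kit when the tablets run out stops at 35 days.

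**What else the Protocol allows.** Down-titration (Section 3.1) and discontinuation criterion 8 (Section 3.3.5.1) respond to hypoglycaemic events. Criterion 2 permits discontinuation for safety. Sections 4.6.2.1 and 4.7.1.2 and Appendices D and E recognise that investigational product can be interrupted or held. None of these provides for replacing a wrong kit.

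**The case against.** The strongest reply is that the sentence is an allocation rule. It stands in the section on assigning treatment, between the ban on forced randomization and the statement about balance. Section 6.3.5 fits this reading, because it re-assigns patients who took the other treatment for the whole 52 weeks. At Visit 3 the rule does no harm. This is probably what was meant, but the text does not say so, and sites dispense 13 more times under the same IWRS.

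Several facts limit the harm and stand in full. The doses are within the protocol range. Capsules were raised because FPG was above target. The glipizide-arm kit contains placebo saxagliptin, so the patient does not take both drugs. Section 4.7.4.1 counts a low glucose value without symptoms as a hypoglycaemic event. It asks for self-monitoring at least every second day in titration and at least weekly afterwards, and tells patients to contact the investigator after a major event or more than one minor event.

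A reader might infer that the site must either leave the kit in place or discontinue the patient. The documents do not support that: the instruction is worded as advice, and product can be held for safety. A reader might also infer that any error found after Visit 3 is hazardous. It is not: a wrong kit given at Visit 3 and found later was titrated from 5 mg. The dose jump needs a cross-arm kit *dispensed* at Visit 4 or later to a patient on at least 2 capsules. Nor is the exposure open-ended, since the next supply is again assigned through the IWRS.

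**Conclusion.** The point holds as a minor one. Section 3.5 fixes a rule that is reasonable for the Visit 3 allocation but, as worded, also keeps a known wrong resupply kit in use, at odds with the 5 mg start in Section 3.1. The size is 10 to 20 mg/day of untitrated glipizide in a saxagliptin-arm patient, or loss of glipizide in the other arm. It lasts at most 21 days in titration (31 at the window limits) or 35 days at 4 capsules/day after Week 18, and 0 days if the error is found at the next visit.

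These figures assume one wrong kit, opened when dispensed, with the patient following the written rule and not having product held. The frequency of such errors is not given and is presumably low. Nothing here supports an inference that the HbA1c comparison is affected, and none is made.

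**What to change.** In Section 3.5, limit the no-correction sentence to the treatment allocated at Visit 3, and add:

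*If at a later visit the kit dispensed differs from the kit number assigned by the IWRS, the patient stops it when the error is found and receives an assigned kit through the IWRS, whatever the kit held. The site informs the IWRS company and the sponsor, checks glucose, and records the kit number and dates as a protocol deviation. The investigator, still blinded, sets the capsule count on resumption from the glucose values.*

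Applying this to every mis-numbered kit keeps the blind: the site learns that a kit was wrong, not which arm it came from.

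A mandatory restart at one capsule is not advised. It would under-dose glipizide patients, including those whose mis-numbered kit held the right drug. After Week 18 it would also collide with the bar on up-titration in Section 3.1. For the same reason, a lower count chosen by the investigator after Week 18 could not be raised again, which should be weighed when resuming.

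The cost is a short text change, plus notification, resupply and a glucose check for a few patients.
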